Aim 2: Self-reported dietary intake will be tracked using MyFitnessPal to determine if daily 5-HTP supplementation influences eating behaviors.

Aim 3:

Methods: Subjects were randomized into a treatment (100 mg 5-HTP daily; CLEANMOOD™) or a placebo (maltodextrin). Body composition was assessed pre- and post-treatment after eight weeks via a multi-frequency bioelectrical impedance device (InBody® 270). Subjects were instructed to not change their training or eating habits; moreover, they were instructed to track their diet ~2-3 days per week using a mobile app (MyFitnessPal).

Hypothesis:

Compared to placebo, daily supplementation with 5-HTP will result in changes in body composition.

Background

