are no studies that have assessed the effects of 5-HTP in exercise-trained individuals. Therefore, the purpose of this investigation was to determine the effects of supplementing with 100 mg daily of 5-hydroxytryptophan (5-HTP) on indices of body composition in exercise-trained men and women.

Study Objectives

Primary Objective

To assess changed in body composition.

Secondary objective

To assess any changes in dietary intake.

Study Methods

Study Design

This study followed a placebo (PLA)-controlled, double-blind and parallel-group design.

Study population

61 physically active, healthy, adults (>18) were volunteered for this study.

Inclusion-Exclusion Criteria

Inclusion Criteria:

- Healthy or free of disease
- Minimum of 1 year of regular physical activity. Regular physical activity is defined by a minimum of 150 minutes of aerobic activity or performing muscle-strengthening exercises at least 2 days a week.

Exclusion Criteria:

- Physically inactive
- Regularly used sleep aids of any kind
- Currently taking selective serotonin reuptake inhibitors (SSRIs) and/or 5-HTP containing supplements.

Discontinuation or Withdrawal from Study

The reasons a subject may discontinue or be withdrawn from the study include, but are not limited to, adverse events, non-compliance or personal request to no longer participate in study.

Randomization and Blinding

All subjects and investigators were blinded. The supplement and placebo were in similar in capsule appearance and were packed in unmarked packaging. The research team were unaware of the subject assignments until completion of the entire study.

Intervention and Placebo

The dietary supplement (100 mg of 5-hydroxytryptophan; CLEANMOOD™) was provided by NURA™ (Irvine, California USA). CLEANMOOD is an organic 5-Hydroxytryptophan (5-HTP) ingredient. The placebo consisted of maltodextrin in a capsule. Subjects were instructed to consume one capsule daily at their convenience for 8 weeks.

Data Collection Schedule

Subjects were instructed to arrive at the laboratory after a 3-hour fast. All pre and post-testing occurred between 1200 and 1700 hours.

Protocol name: Effects of Daily Supplementation of 5-HTP on Body Composition, a Randomized Investigation
 Protocol Version 2
 Document Date: 01/03/2022
 Principal Investigators: [name] PhD FNCSA FISSN CSCS and [name] MS RD

| Study Visit | Pre/Baseline | Post |
|--|--------------|------|
| Informed Consent | x | |
| InBody | x | x |

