| Vitals | x | x |
| Supplement Instruction | x | |
| Connect MyFitnessPal account | x | |
| Asses dietary intake via MyFitnessPal | x | x |
| Asses Compliance (number of pills remaining) | | x |

Missing Data

Thirteen subjects were excluded from the data set due to lack of compliance or failure to complete the study.

Statistical Analysis

All data is presented as the mean+SD. GraphPad (Prism 8) software was used for statistical analyses. A t-test was used to determine if statistically significant differences ($p < 0.05$) existed between the delta scores of the treatment versus the placebo.

Summary of Study Data

Demographic and Baseline

The characteristics of the treatment and placebo groups were as follows (age: 5-HTP 30 ± 10 , placebo 29 ± 11 ; height cm: 5-HTP 171.0 ± 8.7 , placebo 167.7 ± 15.0 ; body mass kg: 5-HTP 72.9 ± 13.4 , placebo 69.1 ± 11.9). Subjects in this investigation were exercise-trained (years of training: 5-HTP 14 ± 10 , placebo 16 ± 11 ; hours of resistance training per week: 5-HTP 5 ± 2 , placebo 5 ± 3 ; hours of aerobic training per week: 5-HTP 5 ± 4 , placebo 6 ± 5).

FDA Annual Reporting

This study is not a FDA regulated drug or device, therefore there are no annual reporting requirements to the FDA.

Clinical Trial Data Bank

The study will be registered on <http://clinicaltrials.gov> and the NCI CTRP (Clinical Trials Reporting Program) by the Clinical Trials Office.

References

1. Birdsall, T.C., *5-Hydroxytryptophan: a clinically-effective serotonin precursor*. *Altern Med Rev*, 1998. **3**(4): p. 271-80.
2. Maffei, M.E., *5-Hydroxytryptophan (5-HTP): Natural Occurrence, Analysis, Biosynthesis,*

Protocol name: Effects of Daily Supplementation of 5-HTP on Body Composition, a
Randomized Investigation

Protocol Version 2

Document Date: 01/03/2022

Principal Investigators: [name] PhD FNCSA FISSN CSCS and [name] MS RD

- Biotechnology, Physiology and Toxicology*. Int J Mol Sci, 2020. **22**(1).
3. Halford, J.C., et al., *Serotonergic anti-obesity agents: past experience and future prospects*. *Drugs*, 2011. **71**(17): p. 2247-55.
 4. Yabut, J.M., et al., *Emerging Roles for Serotonin in Regulating Metabolism: New Implications for an Ancient Molecule*. *Endocr Rev*, 2019. **40**(4): p. 1092-1107.
 5. Cangiano, C., et al., *Effects of oral 5-hydroxy-tryptophan on energy intake and macronutrient selection in non-insulin dependent diabetic patients*. *Int J Obes Relat Metab Disord*, 1998. **22**(7): p. 648-54.

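### The t-test on change has no term for sex in a mixed-sex sample of about 48; adding sex to the model is a cheap, modest improvement

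*Combined protocol and SAP*

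**What the plan says.** The end of the Background states the aim as the effect of the supplement "on indices of body composition in exercise-trained men and women", so both sexes are analysed together. The Methods paragraph of the Abstract says "Subjects were randomized into a treatment" or a placebo. Randomization and Blinding covers blinding, capsule appearance and packaging; it gives no ratio, sequence method, blocking or stratification factor.

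The Statistical Analysis section names one test, a t-test at p < 0.05 for differences that "existed between the delta scores of the treatment versus the placebo". No covariate or stratum is mentioned.

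On numbers, Study population says "61 physically active, healthy, adults (>18) were volunteered for this study" and Missing Data says "Thirteen subjects were excluded from the data set due to lack of compliance or failure to complete the study". Neither figure is split by arm or by sex. Demographic and Baseline lists age, height, body mass, years of training and weekly resistance and aerobic hours by arm, including "body mass kg: 5-HTP 72.9 ± 13.4 , placebo 69.1 ± 11.9". It does not count men and women.

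**The concern.** Sex can be used in three places: to balance the allocation, to adjust the comparison, and to let a reader check that the arms are comparable. The documents mention it in none of them. With about 24 subjects per arm, a noticeable difference in sex mix can arise by chance. Exclusions after enrolment could add to it.

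If men and women change differently in lean or fat mass over eight weeks, part of an observed arm difference could reflect the sex mix. The unadjusted test would also carry the between-sex variation in change as noise. Sex is presumably known for every subject, so the model can use it at almost no cost.

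**Working it through.** The plan has no sample-size, power or effect-size figure, so there is none to reproduce.

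**Inputs from the documents.** 61 enrolled (Study population) and 13 excluded (Missing Data), so 61 − 13 = 48 analysed; 13/61 = 21.3%. The test is a t-test on change at 0.05 (Statistical Analysis).

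**Assumptions.** 24 per arm (48/2), a two-sided test, 40 to 60% men, and a sex difference in mean change, g, of 0.25, 0.5 or 0.75 within-sex SD. The documents give none of these.

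**Step 1: what survives the change score.** A sex difference in level that is the same before and after cancels in post minus pre. Hence

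shift in arm difference = (gap in proportion of men) × g.

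**Step 2: how often a sizeable gap arises.** Exact hypergeometric allocation of 48 subjects into 24 and 24, gap of at least 25 points:

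| Men among 48 | P(gap ≥ 25 points) |
|---|---|
| 24 (50%) | 14.8% |
| 20 or 28 (42%, 58%) | 14.2% |
| 19 or 29 (40%, 60%) | 7.5% |

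Most of the spread comes from whether the number of men is even or odd. With an even number, 6/24 = 25 points is attainable; with an odd number the next attainable gap is 7/24. A 20/28 split of the arms with 24 men also gives 14.2%.

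**Step 3: size of the shift at 15 versus 9 men.** Gap = (15 − 9)/24 = 0.25. The standard error of the arm difference, in within-sex SD, is √(2/24) = 0.289.

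| g (SD) | Shift = 0.25 × g (SD) | Shift / 0.289 | Type I error, t-test, given this gap |
|---|---|---|---|
| 0.25 | 0.06 | 0.22 | about 5.3% |
| 0.5 | 0.13 | 0.43 | about 6.4% |
| 0.75 | 0.19 | 0.65 | about 7.7% |

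The last column comes from simulating the actual t-test. Independent runs gave 5.2 to 5.3%, 6.2 to 6.4% and 7.6 to 7.7%. A shortcut that holds the standard error at 0.289 with a normal cut-off gives 5.5%, 7.2% and 10.0%. That is too high, because the pooled SD of the t-test also grows with g.

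**Step 4: average over randomisations.** With 24 men and 24 women, the t-test's simulated type I error is 4.8 to 5.0% for g from 0 to 0.8. Excess error in unbalanced allocations is offset by conservatism in balanced ones (4.2% at g = 0.5 with no gap). A model with arm and sex stays between 4.7% and 5.1% at every gap examined.

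**Step 5: variance carried by the unadjusted test.** With half men, the share of the variance of change due to sex is (g²/4)/(1 + g²/4), or 1.5%, 5.9% and 12.3% for the three values of g.

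**Step 6: what the baseline data show.** Body mass: t = (72.9 − 69.1)/√((13.4² + 11.9²)/24) = 3.8/3.66 = 1.04, p = 0.30. Height: 171.0 − 167.7 = 3.3 cm, p = 0.36.

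**The case against.** The best defence is that the stated test is sound. Under randomisation an unadjusted t-test on change is unbiased and keeps its level, and Step 4 bears this out. The raised error rates apply only to an imbalance that nobody has observed and a sex difference in change that the documents do not give. Subjects were told to keep their training and eating habits, and nothing in the text suggests that men and women would drift apart over eight weeks. All of this stands, and it keeps the point modest.

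A reader might infer that any sex imbalance passes in full into the arm difference. It does not: level differences cancel, and a 25-point gap passes on one quarter of a difference in change. A reader might also take the heavier 5-HTP arm as a sign of more men there. A difference with t about 1.0 is ordinary chance variation, and turning kilograms into a sex share needs a male–female mass difference that the documents do not supply. Nor do they show that allocation was unstratified; they only describe no stratification.

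Two further objections stand in part. The outcome's own baseline is arguably the more direct covariate, but it can enter the same model and does not make sex redundant. The document is in the past tense and reports completed exclusions, so a sex term added now may be post hoc. That affects its label, not its usefulness.

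One consideration runs the other way. The analysed set remains after 13 exclusions with no split by arm or sex, so its sex balance is not protected by randomisation alone.

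**Conclusion.** The point holds as a modest improvement to the analysis. The plan pools the sexes, describes no stratification and tests change without a sex term. Under the assumed 24 per arm, a 25-point gap in sex share is plausible (about 7 to 15% of allocations). For the assumed sex differences in change it moves the arm difference by 0.06 to 0.19 SD, with conditional type I error of about 5.3% to 7.7%. For scale, the difference detectable with 80% power at 24 per arm is about 0.83 SD.

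The documents do not support calling the t-test invalid, its overall error rate inflated, or the arms in fact unbalanced by sex. If change does not differ by sex, nothing is distorted. The missing sex counts are, on their own, a reporting gap; the substance of the point is the covariate.

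**What to change.** Analyse change with a linear model containing arm and sex, and report the arm coefficient with its 95% CI. If outcome data have already been seen unblinded, keep the stated t-test and present this model beside it as a sensitivity analysis, labelled as such. Report the number of men and women per arm, among those randomised and among those analysed, and state whether allocation was stratified.

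The cost is one degree of freedom and one line in the baseline summary. If change does not differ by sex, adjustment under imbalance loses a little power. With half men and a 25-point gap, the variance of the arm estimate grows by 1/(1 − 0.25²) = 1.067, which takes power from about 80% to about 78% at a true difference of 0.83 SD.
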